To accomplish these goals, our outpatient clinic is open Monday thru Friday offering 4 different appointment times. All patients that are referred to our clinic for TAP, first receive a vein evaluation to see if the patient is a candidate for peripheral IV therapy. At our clinic, approximately 68% of our TAP's are performed peripherally. This eliminates the risk of a central line infection and any alteration in activities of daily living, such as bathing(Kramer, 2016), (Shang, Ma, Poghosyan, Dowding, & Stone, 2014),(Keller et al., 2018; McDiarmid, 2015).

Our hypothesis, is that the 20-gauge BD Nexiva Diffusics catheter provides the same efficacy as current practice with no increase in adverse events for patients undergoing therapeutic apheresis. The results from our study will be significant because if the 20 guage needle is equally effective for TAP, it can increase the number of patients that would be candidates for peripheral therapy. Therefore, decreasing the need for central venous access, which place the patient at an increased risk of infection. Our study is a comparison of 2 types of infusion catheters. The standard of care is an 18-gauge autogard catheter (control group) which will be compared to the 20-gauge BD Nexiva Diffusics (intervention).

- P patients who require therapeutic apheresis procedures (TAP)
- I use of 20G BD diffusics catheter during apheresis
- C use of 18 G standard of care IV catheter during apheresis
- O no difference in efficacy and no increase in safety events

Concise Summary of Project

This is a randomized pilot study of TAP using the current standard of care catheter (SOC) vs the BD Nexiva Diffusics Catheter. It is a single blinded, randomized study. Data will be used to refine and power a full randomized control trial. For this study, a sample of 33 encounters in each group (total of 66 encounters). Our specific aim is to test the hypothesis that the 20-gauge BD Nexiva Diffusics Catheter provides the same efficacy and lower pain level with no increase in adverse events for patients undergoing apheresis treatments.

Randomization Procedure

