After an eligible participant is consented to the study the patient will be randomized without replacement to the use of one of the two catheters. Using a random number generator, numbers between (1-66) were randomly divided into two groups: SOC Control group and BD Intervention group (Figure 1). A study identification number (SID) key will be saved on a UTSW approved secure device and only the research coordinator will have access to the SID key showing which SID coordinates with each group. This will ensure that unblinding can occur is necessary and there is a backup to randomization.

The research coordinator will have 66 randomized envelops without replacement. Half of the envelops will be assigned to 18G catheter SOC (control) and the other half be assigned to

20G BD Nexiva Diffusics catheter (intervention). The PI will be blinded, therefore the PI will pick an envelope when patients are consented and ready for treatment. Participants will be randomized after they have consented to the study. Participants' will then be randomized to one of the two groups again at each encounter (i.e., SOC visit). Inside the envelope it will tell the investigator if the patient is in the control or intervention group of the study.

To promote a more representative sample, each patient may participate a maximum of 10 times.

Study procedure:

[figure not shown]
Each enrolled patient will participate in the study will be randomized at each encounter. During each encounter the following information will be captured:

- 1. CBC
- 2. Patient discomfort

level with placement of catheter

- 3. Inlet rate
- 4. Return line pressures
- 5. Procedures alarms
- 6. Procedure total time
- 7. Post procedure sample

Treating nurse (RN) will start the TAPs procedure with one of the 2 catheters. During the intervention period, the RN will be at bedside during as it is SOC in the Apheresis unit however for the purpose of this study the RN will have the study data collection form (DCF, Appendix1). The RN will complete the pre-assessment including a pain assessment to establish pain level prior to procedure that is currently documented in the electronic medical record. The patient will be asked to self-report the pain level after the return line has been started on the visual analog scale (VAS) Scale from 0mm to 100mm "0 being the lowest/ no pain, 100mm being the highest

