level of pain". The VAS scale will be used for both the SOC and intervention group to compare the pain level when starting the return line. The RN will collect a CBC before the start of the procedure which will be used in the programing of the TAP procedure. The RN will start recording the "inlet rate, return line pressures, and alarms" every 15 minutes until the procedure is completed.

Before patient disconnects, and after the completion of procedure sing the same therapeutic apheresis procedure access site, a blood sample will be drawn by the RN 2 lavender top tubes (4ml) for plasma hemoglobin test. The plasma hemoglobin test will be sent to the UTSW lab for analysis of hemoloysis and results will be sent back directly to the PI. Blood sample results will be collected by the PI or the study team in an excel spreadsheet (CRF) that will be saved on a secure drive on the UTSW campus.

Hemolysis is defined as the destruction of red blood cells which leads to the release of hemoglobin from the red blood cells into the blood plasma. Each patient will be tested for hemolysis by running plasma hemoglobin test after the procedure has finished. This will be collected in a two lavender tops (4ml) The cost for this test is covered by sponsor and because the patient has an indwelling access to venous blood there will no charge for drawing the sample.. There is no clinical suspicion that the use of the 20-gauge BD Nexiva Diffusics Catheter will increase this risk. Hemolysis will be scored dichotomously as present or absent for each encounter.

Pain is defined as any increase discomfort experienced by the patient associated with the apheresis procedure. The current standard of care is to ask the patient "are you having pain" and then ask them to rate the pain from 0 to 10. For this study, one additional question will be asked after the patient's vein has been accessed (IV catheter in place). The patient will self-report their pain using a 100 mm VAS scale. "*The VAS has been used by healthcare providers to measure the characteristics of disease severity in each patient individually*"(Klimek et al., 2017) Currently, all peripheral apheresis patients have some pain/discomfort while having a treatment, however; it is usually tolerated with minimal complaints.

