efficacy wherein efficacy is represented by 1) the plasma hemoglobin value, and 2) the amount of time (minutes) required to complete a TAP. Hence models will be constructed to compare the mean plasma hemoglobin values by group, and to compare the mean number of minutes to complete TAP by group. Second, ANOVA will be used to compare the mean number of adverse events subjects experience in each group (intervention vs control).

Finally, a planned secondary analysis is to examine if the percent of lumen occupied by the return catheter is associated with return pressures. The suggested standard is that a catheter occupies < 45% of the inner-lumen diameter (measured with ultrasound). Return pressures >400 mm Hg are considered problematic. Chi-square analysis will be used to explore the odds of experiencing a return pressure > 400 mm Hg when the return catheter occupies <45% of the inner-lumen diameter.

Item	Month 1-2	Month 3-6	Month 4-8	Month 9-11	Month 12-18
IRB approval	Х				
Consent/	Х	X			
Enrollment					
Randomization	Х	X	Х	Х	
Data collection	Х	Х	Х	Х	
Manuscript				Х	X
prep					
Study closeout					X

Project Timeline

Enrollment of first patient (month 1), enrollment of the last patient (month 12), completion of data analysis (month 14), and manuscript submission (month 18). The apheresis team see approximatley 3000 TAP treaments each year. Of these, approximately 1500 encounters will meet the primary inclusion criteria. We anticipate that it will take less than 1-year to complete the study.

Future directions

The intention of this pilot study is to test the 20-gauge BD Nexiva Diffusics Catheter performance and efficacy. The findings from this study will be used to provide additional preliminary data to BD to support a National Institutes of Health or Agency for Healthcare Research and Quality (AHRQ) application (pending 2017 AHRQ funding announcements). Stakeholder feedback will be provided through an optional de-identified report to all patients and families.

Presentation of data

It is anticipated that the results from this study will be presented to American Society for Apheresis at their annual convention. The results will also be summarized in a manuscript and submitted for peer-review publication to Journal of Clinical Apheresis.

Appendix 1

Patient Sticker

A Randomized Trial Examining Plasma Exchange using the BD Catheter In an Outpatient Apheresis Unit The "REPLACE" study

Date SID Procedure Type						

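### The secondary analysis of lumen occupancy and return pressure cuts two continuous measures into a 2x2 chi-square, which costs about half or more of the power at a moderate correlation and ignores repeated encounters within patients

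*Combined protocol and SAP*

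**What the plan says.** The closing paragraph of the Statistical Analysis Plan sets the aim: to "examine if the percent of lumen occupied by the return catheter is associated with return pressures". It gives a short reason for each cut: "The suggested standard is that a catheter occupies < 45% of the inner-lumen diameter", with the diameter taken by ultrasound, and "Return pressures >400 mm Hg are considered problematic". The only method named is "Chi-square analysis will be used to explore the odds of experiencing a return pressure > 400 mm Hg" when occupancy is under 45%.

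The data behind it are richer and more structured than a 2x2 table:

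- Under Study procedure, inlet rate, return line pressure and alarms are recorded "every 15 minutes until the procedure is completed".
- The form in Appendix 1 records vein diameter under three conditions (with tourniquet, without it, and with the procedure running).
- The Concise Summary of Project plans "a sample of 33 encounters in each group (total of 66 encounters").
- Under Randomization Procedure, participants are "randomized to one of the two groups again at each encounter", and "each patient may participate a maximum of 10 times". The recruitment section expects 30 participants.

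The plan gives no patient-level term, no fallback for small cells, no rule for turning serial pressure readings into one yes/no value, and no statement of which vein diameter defines occupancy.

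**The concern.** The question is about association between two continuous quantities, and the planned test discards most of the information in both. An encounter at 44% occupancy is treated as different from one at 46% and the same as one at 20%; a pressure of 399 mm Hg counts the same as one of 150. With 66 encounters there is little information to spare.

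The chi-square also assumes independent encounters. The catheter is randomized afresh each time, but occupancy depends on the patient's vein as well as the catheter. Return pressure may be similar across a patient's visits too. When exposure and outcome both cluster by patient, the test can reject too often.

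At stake is a real association being missed, or a chance one reported. The Concise Summary says the data will be used to refine and power a full trial. An estimated slope with its interval would serve that purpose better than a p-value from a cut table.

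**Working it through.** **The plan's own figure.** 33 + 33 = 66 encounters, which is correct. No power statement exists to reproduce: the documents give no significance level, effect size, rate of pressures above 400 mm Hg, share of encounters at or above 45%, or within-patient correlation. The values below for these are assumptions, shown as ranges.

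**Step 1: clustering structure.** 66 / 30 = 2.2 encounters per patient on average. The cap of 10 would allow as few as 66 / 10 = 6.6, so 7 patients.

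**Step 2: smallest expected cell.** This is 66 × p × q, where p and q are the smaller shares on each margin. It is below 5 when p × q < 5/66 = 0.076.

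| p (pressure > 400) | q (smaller occupancy group) | Expected count |
|---|---|---|
| 10% | 10% | 0.66 |
| 10% | 30% | 1.98 |
| 20% | 30% | 3.96 |
| 30% | 30% | 5.94 |
| 50% | 50% | 16.5 |

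Sparse cells are therefore possible, not established.

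**Step 3: power.** Simulation with n = 66 independent encounters, bivariate normal values, two-sided 5%, 20,000 runs. The continuous analysis is a Pearson correlation test; the cut analysis is a Pearson chi-square.

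| Correlation | Continuous | Median splits | 10% / 30% cuts | 10% / 10% cuts |
|---|---|---|---|---|
| 0.3 | 70% | 35% | 25% | 25% |
| 0.4 | 92% | 57% | 38% | 37% |
| 0.5 | 99% | 78% | 55% | 51% |

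At 0.3 the loss is (70 − 35)/70 = 50% of the power at best and (70 − 25)/70 = 64% with the uneven cuts. At 0.4 it is 38% to 60%; at 0.5, 21% to 48%.

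**Step 4: false positives with independent encounters.** Across the sparse and non-sparse settings tried, the chi-square rejected a true null 2.8% to 5.2% of the time. Sparseness alone did not inflate the error rate.

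**Step 5: false positives with clustering.** Assumptions: vein diameter with mean 3.0 mm and SD 0.6 mm, 60-90% of its variance between patients; catheter outer diameters 1.3 mm (18G) and 1.1 mm (20G); latent outcome ICC 0.2-0.6; 10-30% of encounters above 400 mm Hg; encounters spread evenly over patients.

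The 45% cut then falls at vein diameters of 1.3/0.45 = 2.89 mm and 1.1/0.45 = 2.44 mm. About 43% of 18G and 18% of 20G encounters would be at or above it, or about 30% overall. Rejection rates under no association, at nominal 5%:

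- 30 patients: about 5-8%
- 12 patients: about 5-16%
- 7 patients: about 6-23%

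**Step 6: whether keeping the values continuous is enough.** It is not. With an ICC of 0.5 in both variables, an unadjusted correlation test rejects about 9% of the time with 30 patients and 26% with 7. A patient term is needed as well.

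**The case against.** The strongest reply is that this is one prespecified, exploratory secondary analysis in a pilot, that both thresholds have stated reasons, and that whether the 45% guide separates problematic pressures is a fair practical question. That stands: it limits the weight of the point and is why the table should be kept as description.

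Four stronger readings are tempting, and the documents do not support them:

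- **That the cells will be sparse.** No rate is given for either cut. At 30% on both margins the smallest expected count is 5.94.
- **That the p-value is unreliable because of sparseness.** A single table can look fragile: margins of 6 and 6 with an overlap of 2 give p = 0.030 by chi-square and 0.088 by Fisher's exact test. That is one selected table; step 4 shows no inflation on average. The real threat to the error rate is clustering, which is modest at the expected 30 patients.
- **That most of the power is always lost.** That needs uneven cuts or a weak association. With median splits at a correlation of 0.5, about a fifth is lost.
- **That an encounter counts as positive if any reading exceeds 400 mm Hg, so longer procedures score worse.** The plan states no such rule. The gap is that the summary and the unit of analysis are undefined.

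A further objection concerns the remedy. Under Potential Risks, inlet rate is reduced after repeated alarms and the catheter may finally be replaced. Inlet rate can thus be a response to earlier return problems, and catheter size is itself part of occupancy. Adjusting for either in the main model could distort the slope or change the question. This stands, and the fix below respects it.

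**Conclusion.** The point holds as a recommended change. The analysis does not match its own question: it cuts two continuous measures and names no allowance for repeated encounters. For a correlation of 0.3 the cuts lose about half the power at best and nearly two thirds with uneven splits; for 0.4, about two fifths to three fifths. These figures assume independent encounters, approximate normality and a two-sided 5% level.

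Inflation of the false-positive rate is small (about 5-8%) if 30 patients contribute evenly. It becomes serious only if few patients contribute many visits, which the cap of 10 permits. Those rates rest on the assumed vein, catheter, ICC and event-rate values in step 5.

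A reader might infer that the trial's main result is at risk. It is not: the primary comparison of catheters does not depend on this analysis.

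**What to change.** Replace the chi-square as the main secondary analysis with a linear mixed model (or GEE) of return pressure on continuous percent occupancy. Include procedure type and a random patient effect, adding a random encounter effect if the 15-minute readings are used directly. Report the slope per 10 percentage points and the predicted pressure at 45%, each with a 95% confidence interval.

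State in advance:

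- which of the three recorded vein diameters defines occupancy;
- the unit of analysis and, if one value per encounter is used, the pressure summary (for example mean or maximum);
- that only readings up to any catheter replacement enter the model, since replacement changes occupancy.

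Put inlet rate and catheter type in sensitivity analyses only. Keep the 45%/400 mm Hg table as description, with a cluster-adjusted or exact odds ratio and its interval.

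The cost is SAP wording and a little programming. Pressures, procedure type, catheter type and vein diameters are already on the Appendix 1 form. Catheter outer diameter is not, and must be taken from the device specification.

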Instructions:	Please complete the following form except for the VAS scale. Must be completed by patient to measure the characteristics of pain severity. Please circle option that apply.					
Collect CBC	Yes	Νο				
Catheter type	18 GA BD Autogard	20 GA BD Nexiva Diffusics				
Vein diameter w/tourniquet:	Vein diameter w/o turniquet:	Vein diameter Procedure Running:				
Asses pain after return placement						
Please rate your current pain by drawing a vertical line across the bar below						

vere		Extremely Severe		
		Procedure d	ata	
tart time:				
Inlet rate	Return line pressures	Alarms	Comments	
	tart time:	tart time: Inlet rate Return line	Procedure da tart time: Inlet rate Return Alarms line	

Total Procedure time:	Procedure en	Procedure end time:		Final Inlet Volume/Blood Processed:	
Collect post proceduer Plasma Hemoglobin	Yes		No		

References

- Golestaneh, L., & Mokrzycki, M. H. (2013). Vascular access in therapeutic apheresis: update 2013. *Journal of clinical apheresis, 28*(1), 64-72.
- Kalantari, K. (2012). The choice of vascular access for therapeutic apheresis. *Journal of clinical apheresis*, 27(3), 153-159.
- Keller, S. C., Williams, D., Rock, C., Deol, S., Trexler, P., & Cosgrove, S. E. (2018). A new frontier: Central line–associated bloodstream infection surveillance in home infusion therapy. *American journal of infection control*, 46(12), 1419-1421.
- Kramer, N. (2016). Monitoring Central Line-Associated Bloodstream Infections (CLABSI) in Home Infusion. *Infusion*, 22(4), 35-44.
- McDiarmid, S. (2015). Reduce the risk of infection by reducing the need for central lines: using ultrasound guidance to establish peripheral access in patients with sickle cell disease undergoing red cell exchange apheresis. *Journal of clinical apheresis*, *30*(2), 98-99.

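### The patient alone rates pain, yet the plan does not say whether the patient is blinded and puts the VAS below the catheter-type row, so the pain comparison is open to expectation bias

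*Combined protocol and SAP*

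**What the plan says.** **Blinding.** The Concise Summary of Project gives the label, "It is a single blinded, randomized study", without saying who is blinded. The Randomization Procedure names one party: "The PI will be blinded, therefore the PI will pick an envelope when patients are consented and ready for treatment". The same section says that the contents of the envelope disclose the group to the investigator. No section says that the patient is blinded. None describes keeping the catheter, its packaging, the envelope or the form from the patient.

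**Pain.** Under Study procedure, "The patient will self-report their pain using a 100 mm VAS scale", once the catheter is in place. That section also says that VAS scores will be used to compare the two groups. The specific aim in the Concise Summary includes a lower pain level with the 20-gauge catheter.

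**The form.** The treating nurse has the Data Collection Form at the bedside. Its instruction reads "Please complete the following form except for the VAS scale. Must be completed by patient to measure the characteristics of pain severity". The catheter-type row offers "18 GA BD Autogard" and "20 GA BD Nexiva Diffusics" as options to circle. A row of vein diameters follows, and then the patient's item: "Please rate your current pain by drawing a vertical line across the bar below".

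**Analysis.** The Statistical Analysis Plan specifies comparisons of plasma hemoglobin, minutes to complete the procedure and number of adverse events, and a secondary analysis of return pressure by lumen occupancy. It lists no analysis of the VAS.

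**The concern.** Pain is a self-reported outcome, so the patient is the outcome assessor. Blinding the PI does not protect it. If patients know which catheter they have and expect the smaller one to hurt less, their marks can differ between arms with no difference in the catheters themselves.

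The protocol's own expectation has a direction: Background and Significance suggests that a smaller needle may be less uncomfortable, and Potential Benefits hopes for less pain. Patients are also re-randomized at each encounter, up to 10 times, so a patient who can tell the devices apart can compare visits.

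At stake is whether a lower VAS in the 20-gauge arm can be read as an effect of the catheter. The pilot is meant to refine and power a full trial. If pain were carried forward as an outcome, that trial could be planned on an inflated difference.

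**Working it through.** The point rests on the text. The plan has no figure to reproduce: it gives 33 encounters per group (33 + 33 = 66) with no alpha, power, SD or effect size.

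**Step 1. Who is blinded, and who rates pain?**

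| Question | What the documents give |
|---|---|
| Who is blinded? | Label only in the Concise Summary; the PI named in the Randomization Procedure |
| Who rates pain? | The patient, on a 100 mm VAS (Study procedure; Appendix 1) |
| Is any step described that masks the patient? | No |
| Where is the gauge recorded? | On the Data Collection Form, above the VAS |
| Is the gauge circled before the VAS is marked? | Not stated; the row order suggests it |

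The one party named as blinded does not produce the pain score, and the party who does has no stated protection. Both gauges are pre-printed, so it is the completed circle that would disclose the arm. Nothing prevents the circle from being there when the patient is handed the form.

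**Step 2. Can patients compare catheters?** Recruitment Methods expects 30 participants. 66 / 30 = 2.2 encounters per patient on average, so repeat encounters will be common.

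**Step 3. Which results are exposed?** The between-group VAS comparison (Study procedure) and the lower-pain part of the specific aim. Nothing in the Statistical Analysis Plan feeds the VAS into the tests of plasma hemoglobin, procedure time or adverse events.

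**Step 4. How sensitive would a VAS comparison be?** This is an illustration, not an estimate. Assumptions: 33 independent encounters per arm, two-sided alpha 0.05, no true pain difference, and an average reporting shift d between the arms. Only the 33 comes from the documents; alpha, SD and d are assumed.

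SE = SD × √(2/33) = SD × 0.2462

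P(significant) = Φ(d/SE − 1.96) + Φ(−d/SE − 1.96)

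Example with SD 20 mm and d 5 mm: SE = 4.92 mm and d/SE = 1.016, so P = Φ(−0.944) + Φ(−2.976) = 0.1725 + 0.0015 = 0.174.

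| SD (mm) | d = 0 | d = 3 mm | d = 5 mm | d = 10 mm |
|---|---|---|---|---|
| 15 | 5.0% | 12.8% | 27.3% | 77.3% |
| 20 | 5.0% | 9.3% | 17.4% | 52.8% |
| 25 | 5.0% | 7.8% | 12.8% | 36.9% |
| 30 | 5.0% | 6.9% | 10.4% | 27.3% |

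Here d is an average over all encounters in the arm, including those in which the patient neither knows nor notices the gauge. If, for example, half the 20-gauge encounters were affected by 10 mm each, d would be 0.5 × 10 = 5 mm. The table ignores correlation between encounters of the same patient.

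**The case against.** The strongest reply is that knowledge of the assignment is not shown. The documents do not say that the patient is told the arm: the envelope informs the investigator, and the single-blind label may have been meant to cover the patient. The form does not say that the circle precedes the mark, and the extracted text shows neither page breaks nor how the form is handed over. This stands. A reader might infer that patients rate pain already knowing their catheter; the text supports only that they may.

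The direction of bias is not established either. The remarks about less discomfort are protocol text, and what the consent form says about pain cannot be judged here. The one relevant consent message that the protocol describes is unfavorable to the smaller catheter: the procedure might take longer. This also stands. Bias toward the 20-gauge is plausible and matches the protocol's own expectation, but patient expectation is undocumented.

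Third, the VAS is in neither the primary hypothesis nor the planned tests. That limits the reach of the point but does not remove it, because a between-group pain comparison is announced under Study procedure and lower pain is in the specific aim.

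Finally, patients may recognize the device whatever the form shows, so a new form may remove only part of the problem. This is fair, and it is why the fix includes a guess question. It does not justify leaving the gauge and the VAS together on one form.

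**Conclusion.** The point holds in a limited form. The plan does not state whether the patient, who alone rates pain, is blinded. It describes no step to keep the gauge from the patient, and its form lets the assignment be seen before the VAS is marked. The pain comparison is open to expectation bias of unknown size.

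Under the stated assumptions, a 5 mm average shift would raise a nominal 5% false-positive rate to between 10% and 27%, and a 10 mm shift to between 27% and 77%. These figures show sensitivity only; the documents give neither a shift nor an SD.

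Two stronger readings are not supported. One is that the trial's main results are compromised: the planned tests of plasma hemoglobin, procedure time and adverse events are not affected by this point. The other is that the lower-pain aim cannot be supported at all: a difference would need cautious interpretation, but nothing shows that it must be an artifact. This is a worthwhile low-cost improvement to a declared but non-primary part of the study.

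**What to change.** 1. State in the Concise Summary and the Randomization Procedure who is blinded, whether that includes the patient, and by what means.
2. Take the VAS off the Data Collection Form and put it on a separate sheet carrying only SID, date and encounter number.
3. Have the patient mark that sheet before the catheter-type row is completed.
4. Instruct the nurse not to state the gauge, or show the packaging or the completed form, until the mark is made. Covering the access site is not part of this proposal.
5. After the mark, ask one question: which catheter does the patient think was used? Report the answers by arm beside any pain comparison.

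**Cost.** One extra sheet and one extra question per encounter (66 of each), plus a short nurse instruction. Treatment, sample size and visit schedule do not change. Concealment will be imperfect because patients may see or recognize the device, so any pain difference should be reported with the guess results and interpreted cautiously.
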